[name]. [name]	
 • Providing guidance on the pharmacological rationale for using finerenone in CKD patients. • Offering consultation on interim analyses when needed. • Providing mentorship, fostering a robust academic and research environment. • Assisting in the interpretation of study results and contributing to the preparation of manuscripts for peer-reviewed journals or conference presentations.
Assoc. [name] [name]	
 • Follow up with the researcher • Help in overcoming the obstacles encountered, analyzing the results and performing the appropriate statistical analysis. • Help the researcher in arranging the results and writing the thesis.

Introduction

It has been observed that kidneys and eyes are significantly interlinked, due to the substantial overlaps in pathways of development, structural anatomy, physiological and pathological characteristics (Wong et al., 2014, Elias et al., 2016). For instance, the glomerulus and choroid possess comparable vascular circulation, and similar pathological mechanisms are involved in the development of CKD and many ocular disorders, such as oxidative stress, inflammation, atherosclerosis, endothelial dysfunction and vascular remodeling (Nusinovici et al., 2019). Additionally, both diabetic and non-diabetic kidney disease patients have been characterized by lower thickness of peripapillary and parafoveal retinal nerve fiber layer (RNFL), peripapillary choroidal, and central macular thickness (Balmforth et al., 2016, Basiony et al., 2023, Zeng et al., 2021). The risk of retinal vascular disease (RVD), major eye diseases and impaired vision has been shown to be significantly increased in patients with CKD (Grunwald et al., 2010, Jonas et al., 2017, Lin et al., 2021). Vision impairment and visual loss can be caused by RNFL defects (RNFLDs), which can be non-invasively detected using fundus photography or optical coherence tomography (OCT), and significantly associated with other systemic conditions including CKD (Wan et al., 2024). Accordingly, it has been suggested that ocular manifestations have been shown to be the mirror of CKD development (Benitez-Aguirre et al., 2012, Wong et al., 2004).

Finerenone, a novel orally administered selective non-steroidal MRA demonstrates stronger affinity to the mineralocorticoid receptor (MR) in comparison with eplerenone and spironolactone resulting in better efficacy in aldosterone's inhibition (Palanisamy et al., 2022). As demonstrated by FIDELIO-DKD (NCT02540993; n = 5674) and FIGARO-DKD (NCT02545049; n = 7352) randomized phase 3 trials, slower progression of CKD and reduced risk of cardiovascular outcomes were associated with administration of finerenone versus placebo in patients with CKD and type 2 diabetes (T2D) (Bakris et al., 2020, Pitt et al., 2021). Based on these trials, clinical practice guidelines recommended finerenone as part of the pharmacological treatment to prevent kidney disease progression and cardiovascular events in CKD patients with T2D (de Boer et al., 2022, Blonde et al., 2022). Regarding non-diabetic CKD patients, FIND-CKD trial, a phase 3 randomized controlled trial of finerenone in patients with CKD of non-diabetic etiology, verified the safety and efficacy of finerenone in this population (Heerspink et al., 2024). According to a recent comprehensive review, finerenone possesses different or superior multiple mechanisms of action to traditional MRAs as indicated by both animal and cell-based studies (Zhai et al., 2024).

Regarding vision-threatening complications, it was proven using a mouse model of oxygen-induced retinopathy (OIR) that finerenone reduced the retinal levels of IL-1 β , ICAM-1 and VEGF, vascular leakage, retinal neovascularization as well as the density of retinal microglial cells, while increasing regulatory T cells (Tregs) in the retina, spleen and blood (Jerome et al., 2023). Finerenone has demonstrated beneficial effects in the retina of rodents with diabetes and ischemic retinopathy, reducing the hallmark features of vision-threatening vascular injury including neovascularization, in addition to alleviating retinal inflammation (Jerome et al., 2023). Moreover, positive effects were achieved in patients with non-proliferative diabetic retinopathy according to pooled analysis of two studies from clinical trial participants (ReFineDR/DeFineDR) (Rossing et al., 2023). However, definitive conclusions could not be drawn as the study was exploratory in nature and based on routine ophthalmological examinations. Data reported so far suggest that finerenone might be a potential novel oral treatment for patients suffering from retinal vascular dysfunction. This can be further confirmed by more randomized clinical trials with adequate power based on more comprehensive and accurate functional and structural assessments of retinopathy.

AIM OF THE STUDY

To examine the potential protective effects of finerenone compared to standard treatment (based on patient's symptoms and condition) on retinal vascular dysfunction in CKD patients.

PLAN OF THE STUDY

Study setting: CKD Patients will be recruited from the outpatients' clinics and/or inpatients wards in Alexandria University hospitals and other private hospitals (if possible).

Study design: Open labelled, prospective, two-arm, parallel group, non-placebo controlled clinical trial.

Included patients will be divided into 2 parallel groups randomly.

Treatment arm: will receive oral finerenone in addition to standard treatment.

Initial dose of finerenone will be determined according to eGFR:

eGFR \geq 60 mL/min: 20 mg once daily.

eGFR $>$ 25 mL/min, $<$ 60 mL/min: 10 mg once daily

eGFR $<$ 15 mL/min: use is contraindicated

Maintenance dose will be determined by the serum potassium level measured 4 weeks after initiation of therapy or dose adjustment according to CKD progression.

Control arm: will receive standard treatment according to patient's condition and symptoms.

Type of the trial: Open labelled randomized controlled clinical trial with parallel design.

Inclusion and exclusion criteria

Inclusion criteria

- ✓ Age: above 18 years
- ✓ Diabetic and non-diabetic non-hemodialysis CKD patients (Stage 2 – Stage 4).

Exclusion criteria

- ✓ Patients on hemodialysis (HD).
- ✓ Serum potassium level $>$ 5.5 mEq/L
- ✓ Prior/planned ocular interventions (retinal laser treatment, intravitreal injection or vitrectomy).
- ✓ Pregnant and lactating women
- ✓ Malignancy

Target population: CKD patients.

Sample size: Will be calculated using suitable software to achieve the study objective

Outcome assessment:

Primary outcomes

To elucidate the difference in field vision and optical coherence tomography (OCT) metrics 1 month, 3 months and 6 months after treatment initiation compared to baseline findings; OCT metrics include macular thickness and retinal nerve fiber layer (RNFL) thickness.

Secondary outcomes

- To examine the effect on eGFR slope, defined as the mean rate of change in eGFR from baseline to month 6 of treatment.
- Mean change from baseline scores of routine laboratory investigations of CKD patients including serum creatinine, urea, uric acid, urinary albumin to creatinine ratio (ACR), complete blood count (CBC), and serum albumin.
- Mean change from baseline values of metabolic parameters including random blood glucose (RBG), glycated hemoglobin (HbA1C), lipid profile and liver enzymes (ALT and AST) in addition to mean change in body weight.
- To examine the metabolic regulatory effects exhibited by finerenone by measuring the mean change from baseline levels of adipokine leptin.
- Safety will be assessed at all scheduled visits and includes assessment of vital signs and adverse events. Hyperkalemia is an adverse event of special interest in this study. Serum potassium and hyperkalemia will be characterized through monitoring the change from baseline in serum potassium and identification of the number of patients with serum potassium levels >5.5 mmol/L and >6.0 mmol/L.

Type of sample and method of selection:

Ocular examinations will be performed by expert ophthalmologists in addition to blood and urine samples that will be collected at baseline and after the follow-up duration to conduct laboratory investigations.

Data collection methods and tools:

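### The protocol does not secure its intended comparison: current users of finerenone or another mineralocorticoid receptor antagonist (MRA) may enter, and undefined standard treatment may include finerenone

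*Protocol*

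**What the plan says.** **Arms (Plan of the Study).** The treatment arm "will receive oral finerenone in addition to standard treatment"; the control arm "will receive standard treatment according to patient's condition and symptoms". The protocol does not define standard treatment and names no drug or class as allowed or barred. The trial is open label.

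**Eligibility (Inclusion and exclusion criteria).** The population is "Diabetic and non-diabetic non-hemodialysis CKD patients" in stages 2 to 4. The five exclusions are haemodialysis, high serum potassium ("Serum potassium level $>$ 5.5 mEq/L"), prior or planned ocular procedures, pregnancy or lactation, and malignancy. There is no criterion on current or recent finerenone, spironolactone or eplerenone, and no washout.

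**Place of the drug in care (Introduction).** For CKD with type 2 diabetes, "clinical practice guidelines recommended finerenone as part of the pharmacological treatment to prevent kidney disease progression". Finerenone is described as an MRA that "demonstrates stronger affinity to the mineralocorticoid receptor (MR) in comparison with eplerenone and spironolactone".

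**Outcomes (Outcome assessment).** Visual field and OCT measures are compared with baseline at 1, 3 and 6 months. Most secondary outcomes are also changes from baseline. Hyperkalaemia is the adverse event of special interest.

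**Medication history (Data collection methods and tools).** It is taken by interview from patients who have already been included.

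**The concern.** The trial's question depends on one arm starting finerenone while the other does not take it. That needs an eligibility rule, so that patients start from an untreated baseline, and a comparator definition, so that it is clear what controls may receive. The protocol has neither, and its own Introduction places the test drug within recommended care for part of the population it enrols.

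Three things are at stake. The change-from-baseline outcomes lose their meaning in patients who already take the drug. The between-arm difference shrinks if controls receive it, so a null result becomes hard to read. The potassium comparison becomes hard to attribute if other MRAs are present in either arm. Eligibility and the comparator belong in the protocol, and an analysis plan could not restore an untreated baseline or a lost contrast.

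**Working it through.** There is no stated figure to reproduce: the protocol gives no sample size, power, alpha or expected MRA use. The check is mainly a reading of the sections together.

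**1. What the text allows, by type of patient**

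| Patient | Kept out by a listed criterion? | If allocated finerenone | If allocated control |
|---|---|---|---|
| Already on finerenone | No | Baseline is already treated | Not stated whether the drug continues (no contrast) or stops (a withdrawal comparison) |
| Already on spironolactone or eplerenone | No, unless potassium exceeds 5.5 mEq/L | Two drugs on one receptor, so hyperkalaemia cannot be attributed cleanly | Comparator contains the drug class; hyperkalaemia may come from that MRA |
| Type 2 diabetes, no MRA at entry | No | Intended use | Finerenone may be given as standard treatment, on the Introduction's account |

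The potassium criterion does not close the gap, because MRA users at or below 5.5 mEq/L still enter. The medication history does not close it either, because it follows inclusion and is tied to no criterion.

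**2. Direction of the effect**

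Let Δ be the true effect of finerenone against none.

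- *Controls given finerenone.* If a net fraction f of controls takes finerenone with full effect, the observed difference is Δ(1 − f). This is dilution for any f above 0.
- *Background use of another MRA in both arms.* Let p be the share of users and s the share of finerenone's effect that is lost in a user because the effects overlap. The observed difference is Δ(1 − p·s). With p = 10% to 20%, the loss is 0 if s = 0 (effects add), 5% to 10% if s = 0.5, and 10% to 20% if s = 1. Every p and s here is assumed.

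**3. Illustration of control crossover**

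All inputs are assumptions: two-sided alpha 0.05, 80% power, 1:1 allocation, standardised difference d = 0.5, full effect in crossed-over controls. The formula is n per arm = 2(1.960 + 0.842)² / [d(1 − f)]², rounded up. At f = 0 this is 2 × 7.849 / 0.25 = 62.8, so 63.

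| f | d(1 − f) | n per arm for 80% power | Power with 63 per arm |
|---|---|---|---|
| 0 | 0.50 | 63 | 80% |
| 10% | 0.45 | 78 | 71% |
| 20% | 0.40 | 99 | 61% |
| 30% | 0.35 | 129 | 50% |
| 50% | 0.25 | 252 | 29% |

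As an example of how f could arise, if half the controls had type 2 diabetes and 20% to 40% of those were given finerenone, f would be 0.5 × 0.2 = 10% to 0.5 × 0.4 = 20%. Nothing in the protocol says whether the true f is zero or any of these values.

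**The case against.** The strongest defence is that the intention is clear. Adding finerenone to standard treatment only makes sense if standard treatment omits it. The protocol also sets a starting dose, a potassium check four weeks after the drug is begun, and outcomes timed from the start of treatment, all of which presuppose new starters. This stands as evidence of intent. A reader might infer that the trial does not compare finerenone with no finerenone at all; the documents do not support that. They permit finerenone in controls but do not plan it.

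The second defence is that randomisation balances stable use of older MRAs in expectation, that adding a drug to background therapy is a legitimate comparison, and that a stable drug's effect is largely in the baseline already. The Introduction also says that finerenone's mechanisms differ from those of older MRAs, which argues against complete overlap. This stands too: background MRA use need not bias the contrast towards zero. It does not answer open-label prescribing to controls after randomisation, nor the attribution of hyperkalaemia.

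Third, a guideline recommendation does not show that finerenone is routinely prescribed at these hospitals. That is correct, and it is why a stated percentage loss of effect, which a reader might be tempted to infer, has no support in the documents.

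**Conclusion.** The concern holds as a gap in the protocol: the comparison of finerenone plus standard treatment against standard treatment alone is intended but not secured. The eligibility list, the undefined standard treatment and the guideline statement together allow the test drug or its class into both arms.

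The size cannot be derived. Control crossover dilutes the difference in proportion to its frequency, which could be zero. Background MRA use dilutes it only to the extent that effects overlap. The problems with the untreated baseline and with attributing hyperkalaemia do not depend on those assumptions; they arise for each such patient who enters. The gap should be closed before enrolment, because it cannot be repaired afterwards.

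**What to change.** 1. **Exclusion criteria:** exclude patients already taking finerenone, with the look-back period set by the investigators. State how current users of other MRAs are handled at entry: either excluded, or recorded and balanced across the arms.
2. **Data collection methods and tools:** take the medication history before inclusion, so that the criterion can be applied.
3. **Follow-up:** record every start of finerenone or another MRA in either arm. Keep the patient in follow-up and in the analysis of the randomised arm.
4. **Introduction, Plan of the Study and eligibility criteria:** reconcile these on what standard treatment is for control patients with type 2 diabetes. Which medicines to allow is for the investigators; this point does not say how such patients should be treated.

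The cost is a few lines of text, one concomitant-medication field, an earlier medication interview and the loss of some current users from recruitment. The reconciliation in item 4 needs a clinical decision.

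### The protocol's stated sampling times give finerenone patients an interim potassium test that controls may not have, so a count of patients with hyperkalaemia at any time could be uneven between arms

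*Protocol*

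**What the plan says.** Five parts of the Protocol bear on when potassium is measured.

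- **Type of sample and method of selection.** Laboratory work rests on "blood and urine samples that will be collected at baseline and after the follow-up duration to conduct laboratory investigations". No arm is named, so I take this to apply to both. The RESEARCH TIME LINE (Profiling of patients) agrees: samples at baseline, and selected parameters measured again once follow-up is complete.
- **Exclusion criteria.** "Serum potassium level $>$ 5.5 mEq/L" excludes a patient, so a baseline potassium value is needed in both arms.
- **PLAN OF THE STUDY, Treatment arm.** "Maintenance dose will be determined by the serum potassium level measured 4 weeks after initiation of therapy or dose adjustment"; the sentence then ends with a reference to CKD progression. This is the only interim potassium test named in the protocol. The Control arm entry says only that these patients "will receive standard treatment according to patient's condition and symptoms".
- **Primary outcomes.** The interim visits come from the eye assessments, which are made "1 month, 3 months and 6 months after treatment initiation compared to baseline findings".
- **Secondary outcomes, safety.** "Safety will be assessed at all scheduled visits and includes assessment of vital signs and adverse events". The same bullet continues: "Hyperkalemia is an adverse event of special interest in this study". Potassium is to be described by its change from baseline and by "identification of the number of patients with serum potassium levels >5.5 mmol/L and >6.0 mmol/L". No time point or window is attached to these counts.

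**The concern.** The chance that a patient is ever recorded above a threshold rises with the number of times the patient is tested. If one arm is tested more often, it will show more patients above the threshold even when the true risk is the same. Here the extra test would fall in the finerenone arm, so the error would make the drug look less safe on the one adverse event that the protocol singles out.

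Sampling times belong in a protocol. An analysis plan, which may exist but is not shown, could restrict the comparison to times shared by both arms. It could not recover interim control samples that were never drawn.

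**Working it through.** **Step 1: count the post-baseline tests under each reading.** I take the end of follow-up to be month 6, the last time named for the eye outcomes and for the eGFR slope.

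| Reading | Finerenone | Control |
|---|---|---|
| Literal: sampling sentence, timeline and finerenone dosing text | week 4, month 6 (2 tests) | month 6 (1 test) |
| Safety bullet taken to mean potassium at every visit in both arms | months 1, 3, 6 (3 tests) | months 1, 3, 6 (3 tests) |

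In the second row the 4-week dosing test is taken as the month-1 sample.

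**Step 2: inputs for an illustration.** The protocol gives no hyperkalaemia rate, no within-patient correlation and no sample size, so there is no figure to reproduce. Everything below is assumed: an equal risk p = 3% per test of exceeding the threshold in both arms, within-patient correlation r from 0 to 1, and a patient counted if any post-baseline value exceeds the threshold.

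**Step 3: formula.** For independent tests, P(at least one of k) = 1 − (1 − p)^k. For correlated tests, treat the potassium values as equicorrelated normal with threshold c = Φ⁻¹(1 − p). Then P(at least one of k) = 1 − ∫ Φ((c − √r·z)/√(1 − r))^k φ(z) dz.

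**Step 4: literal reading, 2 tests against 1.** At r = 0: 1 − 0.97² = 0.0591, and 0.0591/0.0300 = 1.97.

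| r | Control, 1 test | Finerenone, 2 tests | Ratio |
|---|---|---|---|
| 0 | 0.0300 | 0.0591 | 1.97 |
| 0.5 | 0.0300 | 0.0540 | 1.80 |
| 0.7 | 0.0300 | 0.0496 | 1.65 |
| 0.9 | 0.0300 | 0.0419 | 1.40 |
| 1 | 0.0300 | 0.0300 | 1.00 |

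With p varied from 2% to 5% and r from 0 to 0.9, the ratio runs from 1.36 to 1.98. A different model, beta-binomial with correlation 0.5 between the exceedance indicators, gives 0.0298/0.02 = 1.49 at p = 2%, 0.0738/0.05 = 1.48 at 5% and 0.145/0.10 = 1.45 at 10%.

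**Step 5: allow for dose titration.** The 4-week result is used to set the dose and may lower later risk. Suppose finerenone risk is 3% at week 4 and 1.5% at month 6, against 3% for control at month 6. At r = 0: 1 − 0.97 × 0.985 = 0.0446, ratio 1.49. At r = 0.5, 0.7 and 0.9 the probabilities are 0.0414, 0.0384 and 0.0334, and the ratios 1.38, 1.28 and 1.11. The count still points against finerenone although its month-6 risk is half that of control.

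**Step 6: both-arms reading, 3 tests against 3.** At equal risk per test the ratio is 1.00 for any p and r.

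**The case against.** The strongest objection is that the literal reading may not be the intended one. Potassium appears inside the safety bullet. That bullet opens with every scheduled visit, names no arm and speaks of monitoring potassium. The routine and metabolic laboratory items and leptin are separate bullets framed as change from baseline, and the two-time sampling sentence fits those well. The timeline mentions only selected parameters. On this view both arms have potassium at months 1, 3 and 6, and no imbalance remains. This reading is plausible, but the text does not state it. The visit sentence names vital signs and adverse events rather than a blood draw, the sampling sentence has no interim time, and months 1 and 3 are written only for the eye assessments. A site could follow the protocol and draw no interim control sample.

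Second, inflation requires a rule that counts any post-baseline value. The protocol states no such rule, and an analysis plan might choose another. That stands, and it makes the harm conditional. A month-6-only count and the change from baseline to the end of follow-up would be unaffected.

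Third, the rates and correlations are assumptions, and their range includes no effect. That also stands; the figures show a mechanism and do not estimate a bias.

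A reader might go further and infer that finerenone patients also have a potassium test after each dose adjustment, so that an imbalance remains even if both arms are tested at every visit. The sentence does not settle this. Its closing words on CKD progression allow dose adjustment to be a second route to the maintenance dose rather than a trigger for another test. Nor do the documents establish that controls go untested between baseline and month 6; they leave it open.

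**Conclusion.** The point holds in a limited form. The stated sampling times, followed as written, give at least two post-baseline potassium values on finerenone and one on control. An ever-above-threshold count would then be inflated by a factor of about 1.4 to 2.0 at an assumed 3% risk per test and correlation 0 to 0.9. The factor falls to between 1.11 and 1.49 over the same correlations if titration halves the later finerenone risk. It is 1.00 if potassium is in fact drawn in both arms at every visit. No weight is placed on a test after dose adjustment.

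Severity is minor to moderate. One secondary safety count is at risk, although it concerns the event of special interest, and the error would overstate the drug's harm rather than hide it. The visual field and OCT primary outcomes are untouched.

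**What to change.** State in the protocol that serum potassium is drawn in both arms at baseline and at the existing 1-, 3- and 6-month visits, with the month-1 sample serving as the finerenone dosing test. Base the between-arm counts above 5.5 and 6.0 mmol/L only on these shared times, and list any other potassium values separately by arm.

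On the literal reading this adds a routine potassium sample at months 1 and 3 in controls and at month 3 in finerenone patients, at visits already held for the eye examinations. If the safety bullet was meant to cover potassium in both arms, the change is one of wording only.

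If control samples are not added, compare the arms at month 6 only and report the 4-week finerenone values descriptively. This needs no extra blood but gives up the early comparison between arms.
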